## **Operational Definitions**

### **Oral Hygiene-Related Behaviors:**

Participants' reported frequency and quality of oral health practices, including brushing, flossing, gingival health, and dental visits, measured on a scale of 0(never) to 4(always) using performance related questions. Higher scores will indicate better oral hygiene related behaviors. Pre and post intervention scores were compared, and cutoff levels were determined using the mean and standard deviation (SD).(7)

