### **Perceived Benefits:**

Participants' beliefs about the positive outcomes of engaging in oral hygiene behaviors, such as prevention of oral complications. Assessed using Likert-scale items from 1 (Strongly Disagree) to 5 (Strongly Agree). Higher scores reflect

stronger perceived benefits. Pre and post intervention scores will be compared, and categorization will be done using the mean and SD. (7)

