**Cues to Action:**

Factors which include both Internal and external that motivate participants to involve in oral hygiene behaviors, such as family encouragement or healthcare provider advice. Assessed using a Likert scale. Higher scores denote stronger cues to action. Comparison of pre and post scores were done using the mean and SD for cutoff classification. (7)

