### **Sampling Technique and Randomization**

A convenience sampling technique was used to recruit participants from the outpatient diabetes clinic at DUHS. Patients who are present at the clinic for their routine appointments and meet the eligibility criteria was approached. They were informed about the study objectives and procedures, and those who agreed to participate was asked to provide written informed consent. After enrollment, participants were randomly assigned to either the intervention group or the control group, following a 1:1 allocation ratio. The randomization process was stratified based on three key characteristics including gender, educational level, and duration of diabetes, to ensure balanced distribution and to minimize potential bias.

Randomization was conducted using random number generator where each participant was assigned a random number, then participants were allocated equally into either Intervention Group which received HBM based education via WhatsApp or control Group which received an educational brochure. This study was single blinded in which participants were not informed about the presence of two distinct groups; they were only aware about receiving education related to oral health.

[figure not shown]

Figure 3.1. Flow diagram of patient selection and allocation into intervention and control groups

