## Sample Size

Sample size was calculated using OpenEpi online software, based on two independent sample t-test by using mean and standard deviation of post intervention perceived susceptibility score

which were  $4.09 \pm 0.49$  in intervention group and  $3.64 \pm 1.01$  in control group in the study conducted by Malekmahmoodi et al. (2020)(7). A sample size of 49 achieved in each group, power 95% with a significance level (alpha) of 0.01. Total 98 patients have been recruited and divided into 49 patients in each group (two groups).

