## **Study Duration From date to date**

The study was conducted from July 2025 to December 2025, including participant recruitment, the delivery of the educational intervention, and the completion of post intervention assessments.

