## **Survey Instrument**

A structured, close-ended and self-reported questionnaire with a five-point Likert scale was used. The questionnaire was designed to measure HBM constructs (e.g. perceived susceptibility, severity, benefits, barriers, cues to action, and self-efficacy), awareness of oral health and oral hygiene related behaviors. A panel of four subject matter experts reviewed the instrument, including two dentists, a public health specialist and an endocrinologist. Each expert independently evaluated the questionnaire items by using a four-point relevance scale, ranging from "not relevant" to "highly relevant." Their ratings were used to calculate content validity indices, Items with poor expert agreement ( $I-CVI \leq 0.25$ ) were removed, while items with minor disagreement ( $I-CVI = 0.75$ ) were revised for clarity. Items with strong relevance ratings ( $I-CVI = 1.00$ ) were retained as it is in the final questionnaire. The  $S-CVI/Ave$  for the final instrument was 0.89, which indicates good content validity. The universal agreement index ( $S-CVI/UA$ ) was 0.83, indicating that 83% of the items received unanimous relevance ratings from all four experts.(15)

The final questionnaire consisted of three major sections, designed to assess oral-health knowledge, HBM constructs, and behaviors among individuals with Type 2 Diabetes. Section I comprised of 10 items assessing oral-health knowledge. Section II included the HBM constructs, which was subdivided into

seven domains: Perceived Susceptibility (7 items), Perceived Severity (10 items), Perceived Barriers (6 items), Perceived Benefits (6 items), Self-Efficacy (7 items), Internal Cues to Action (4 items) and External Cues to Action (5 items). Section III was focused on oral-hygiene behaviors, comprising 10 items which measured the frequency and consistency of participants' oral-health behaviors.

The Cronbach's alpha value of the final instrument was calculated after the pilot study in which 30 participants filled the questionnaire which was 0.783. (16)

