## **Data Analysis Procedure**

Data were analyzed through a statistical package for Social Sciences (SPSS) version 26. Frequency and percentages were reported for qualitative variables. Mean and standard deviations were reported for normally distributed quantitative variables while median and interquartile ranges were reported for non-normally distributed quantitative variables. Normality of quantitative variables were assessed using Shapiro-wilk's test of normality. The Independent sample t-test was conducted to compare the mean scores of perceived barriers and behavior between the intervention and control groups. For all other constructs, which were not normally distributed, the Mann-Whitney U test was applied. For within-group comparisons of pre and post scores of behaviors and perceived barriers, the Paired sample t-test was used. The Wilcoxon signed rank test, was used for the remaining variables that were not normally distributed. Stratification was carried out based on gender, diabetes duration, and education level to see the effect of these modifiers on outcome (control vs. intervention) using Chi-square test. A p value less than and equal to 0.05 was considered as significant.

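### The chi-square test named for effect modification by gender, diabetes duration and education does not test whether the effect differs between subgroups

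*Combined protocol and SAP*

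**What the plan says.** The sentence at issue is in Data Analysis Procedure. After naming t-tests and Mann-Whitney tests for the arm comparisons, it says that stratification by gender, diabetes duration and education level was done "to see the effect of these modifiers on outcome (control vs. intervention) using Chi-square test". It does not say which score is meant, what the rows and columns are, or what levels education and duration have.

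Three other places bear on it:

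- **Sampling Technique and Randomization:** the same factors were used in allocation: "The randomization process was stratified based on three key characteristics including gender, educational level, and duration of diabetes".
- **Scoring:** every outcome is a numeric score. Awareness has a maximum of 10, the Health Belief Model constructs run from 1 to 5, and behaviour items run from 0 to 4.
- **Operational Definitions:** the scores may be cut into groups. For perceived benefits, for example, "categorization will be done using the mean and SD". No number of categories and no numeric cutoff is given, and Data Analysis Procedure does not link these cutoffs to the chi-square test.

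**The concern.** A factor modifies the intervention's effect if the arm difference is not the same at its different levels. Testing that requires an interaction term, or a test that the arm effects are homogeneous across strata. The plan states neither. A chi-square test of a single contingency table tests whether its two classifying variables are associated, which is a different question.

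What is at stake is what the report may say about who benefits. If subgroup p-values are set side by side, a reader may conclude that the WhatsApp programme works for one gender or education level and not another when the true effect is the same in both. If the table holds only factor and arm, a non-significant result may be taken as evidence against modification although no outcome was examined.

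**Working it through.** **Inputs.** The plan gives no figure for this analysis. Sample Size gives 49 per arm and post-intervention perceived susceptibility of 4.09 ± 0.49 against 3.64 ± 1.01. The pooled SD is √((0.49² + 1.01²)/2) = 0.794, so the planning effect is (4.09 − 3.64)/0.794 = 0.45/0.794 = 0.567 SD, for one construct only. Alpha is 0.05, from Data Analysis Procedure. (The 49 per arm does not follow from the stated 95% power and alpha of 0.01. That is a separate matter and nothing here depends on it.)

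**Reading 1: factor by arm (the literal wording).** No score enters the table. Take a two-level factor split 66/32 overall. With 35 v 31 patients at the larger level, the expected count is 33 (and 16 at the other level), so χ² = 2 × 2²/33 + 2 × 2²/16 = 0.742 and p = 0.39. With 34 v 32, p = 0.67. For a 49/49 split, 26 v 23 gives χ² = 4 × 1.5²/24.5 = 0.367 and p = 0.54. So if stratified allocation keeps a level within 4 people between arms, p is at least 0.39 whatever the scores show. In simulation with a balanced factor, this test rejected in 0.0% of trials even with opposite effects of +0.8 and −0.8 SD, where an interaction test rejected in 97%.

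**Reading 2: score category by arm, within each stratum.** A hand check on the continuous score with 24.5 per arm per stratum: power is Φ(0.567 × √(24.5/2) − 1.96) ≈ 0.51, so exactly one of two strata is significant with probability 2 × 0.51 × 0.49 ≈ 0.50.

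For the chi-square itself, 40,000 trials were simulated per setting. Assumptions: 49 per arm, two strata, normal scores, equal SDs, a cut at the pooled mean, and the same true effect in both strata. Percentage of trials with one stratum significant and the other not:

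| True effect (SD) | Strata 25/24 per arm | Strata 33/16 per arm |
|---|---|---|
| 0 | 11.9 | 10.7 |
| 0.2 | 18.5 | 17.6 |
| 0.35 | 31.2 | 31.0 |
| 0.567 | 47.6 | 49.7 |
| 0.8 | 46.0 | 53.6 |
| 1.0 | 29.6 | 41.1 |
| 1.2 | 13.7 | 25.1 |
| 1.5 | 2.4 | 8.8 |

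Scores with skewness −1 change these by about 1 percentage point or less. In the same runs an ordinary least-squares interaction test was falsely positive in 4.7–5.2%, and with HC3 robust standard errors in 4.3–4.8%.

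**Reading 3: factor by score category, within each arm.** With the same factor–score association in both arms, the two arms disagree on significance in 8–10% of trials at an association of 0 SD, 41–45% at 0.567, 49–51% at 0.8, 35–44% at 1.0 and 3–10% at 1.5.

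**Reading 4: factor by score category, arms pooled.** This tests whether the factor predicts the score. In 4,000 runs per setting with a median cut, it rejected in 47% with no interaction but a 0.5 SD prognostic effect. It rejected in only 3.5% when the true effects were 0 and 1.14 SD with an offsetting prognostic effect; the interaction test then rejected in 80%.

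**The case against.** The strongest reply is that some chi-square statistics do test heterogeneity. A Breslow-Day test, or a Wald chi-square for an interaction term, would be valid. But the plan names neither and defines no binary outcome for the former. The claim is therefore about the readings the text supports. If such a test was run, stating it would answer the point.

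The second reply is that the simulated percentages rest on choices the plan does not make. This stands in part:

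- Some definitions speak of mean ± SD, which suits three bands at least as well as two. With bands at mean ± 1 SD and equal SDs, discordance is about 9% at 0 SD, 40–43% at 0.57, 43–52% at 1.0 and 8–20% at 1.5.
- With the unequal SDs from Sample Size and the mean cut, it is 46–51% at 0.57 but about 33–43% at 0.8 and 16–28% at 1.0.
- With those SDs and three bands, it is about 45–54% even at zero mean difference.
- A median cut gives about 44% at 0.57.
- Under reading 1, no within-stratum allocation method is described, so a looser balance is possible; 36 v 30 gives p = 0.20.

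The exact percentages are therefore illustrative. The defect does not depend on them.

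Third, modifiers are absent from the objectives and hypothesis, the plan does not say subgroup p-values will be compared, and an added interaction analysis will probably be inconclusive. All true. This limits the importance of the point, but the sentence still names a purpose that its method cannot serve.

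**Conclusion.** The concern holds. On each of the four readings the wording allows, the chi-square test does not address whether the intervention effect differs by gender, diabetes duration or education, and no test that does so is stated.

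Reading 1 carries no information on modification. Under reading 2, at the planning effect of 0.57 SD and with no true modification, about 40–51% of trials show one stratum significant and the other not, across the cutoffs and SDs tried. The figure depends strongly on effect size: with the mean cut and equal SDs it is 11–12% at zero effect and 2–9% at 1.5 SD. It also assumes two strata per factor, since the plan gives no levels.

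The consequence is confined to statements about modifiers. The comparison of the two arms is untouched. It should be fixed, because the sentence invites a conclusion it cannot support.

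**What to change.** Keep the sentence as the record of what was done, say which table was tested, and draw no conclusion about modifiers from it. If the table was factor by arm, label it baseline balance. State the levels used for education and duration.

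Then add wording such as:

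> In a post hoc exploratory analysis, effect modification was assessed one factor at a time by an arm-by-factor interaction in a model of each uncategorised post-intervention score, adjusted for its baseline value, with a method suited to non-normal scores where needed. Every interaction estimate is reported with a 95% CI, and subgroup p-values are not compared.

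The post hoc label is needed because the study is already reported as done: "The study was conducted from July 2025 to December 2025". If the investigators no longer wish to address modifiers, the first paragraph alone corrects the record.

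**Cost.** A few lines of text and a modest analysis of data already collected. Two limits should be disclosed:

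- **Power.** For an interaction of 0.45 points (0.567 SD) and an even two-level factor, the standard error is √(4/24.5) = 0.404 SD, so power is Φ(0.567/0.404 − 1.96) ≈ 0.29. Simulation gave 24–29% unadjusted. Baseline adjustment raises this somewhat, depending on the correlation. About 4 × 98 = 392 patients would be needed for 80%.
- **Multiplicity.** Knowledge, behaviour and six or seven constructs (depending on whether internal and external cues are scored together) make 8 or 9 scores. With three factors and one joint test each, that is 24 or 27 tests, so 24 × 0.05 = 1.20 or 27 × 0.05 = 1.35 false positives are expected if no modification exists.
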